4.1.3 Eligibility Criteria for Open-Label Extension Phase

Patients who meet the following entry criteria may participate in the OLE phase:

- *Either completed 144 weeks of the double-blind treatment phase of the trial or are ongoing in the double-blind treatment phase at the time of the primary analysis and who, in the opinion of the investigator, may benefit from treatment with ocrelizumab*

Patients who withdrew from study treatment and received another disease-modifying therapy (DMT) or commercial ocrelizumab will not be allowed to enter in the OLE phase.

- Able and willing to provide written informed consent to participate in the OLE phase and to comply with the study protocol
- For women of childbearing potential: agreement to remain abstinent (refrain from heterosexual intercourse) or use adequate contraceptive methods during the treatment period and for 6 or 12 months (as applicable by the Ocrevus local label) after the final dose of ocrelizumab.

A woman is considered to be of childbearing potential if she is postmenarcheal, has not reached a postmenopausal state (≥ 12 continuous months of amenorrhea with no identified cause other than menopause), and is not permanently infertile due to surgery (i.e., removal of ovaries, fallopian tubes, and/or uterus) or another cause as determined by the investigator (e.g., Müllerian agenesis). Per this definition, a female participant with a tubal ligation is considered to be of childbearing potential. The definition of childbearing potential may be adapted for alignment with local guidelines or requirements.

The following contraceptive methods are considered acceptable (failure rate $> 1\%$ [CTFG]): (1) progestogen-only oral hormonal contraception, where inhibition of ovulation is not the primary mode of action; (2) male or female condom with or without spermicide; (3) cap, diaphragm, or sponge with spermicide; (4) combination of male condom with cap, diaphragm, or sponge with spermicide (double-barrier method).

Birth control methods that are highly effective (i.e. failure rate $< 1\%$ [CTFG]) may also be used but are not required, and include: (1) oral, intravaginal or

transdermal combined hormonal contraception associated with inhibition of ovulation; (2) oral, injectable or implantable progestogen-only hormonal contraception associated with inhibition of ovulation; (3) intrauterine device; (4) intrauterine hormone-releasing system; (5) bilateral tubal occlusion; (6) vasectomised partner; (7) sexual abstinence.

The reliability of sexual abstinence should be evaluated in relation to the duration of the clinical trial and the preferred and usual lifestyle of the individual. Periodic abstinence (e.g., calendar, ovulation, symptothermal, or postovulation methods) and withdrawal are not adequate methods of contraception.

If required per local guidelines or regulations, locally recognized adequate methods of contraception and information about the reliability of abstinence will be described in the local Informed Consent Form.

For female patients without reproductive potential:

Women may be enrolled if surgically sterile (i.e., hysterectomy, complete bilateral oophorectomy) or post-menopausal (i.e., spontaneous amenorrhea for the past year confirmed by a FSH level > 40 mIU/mL), unless the patient is receiving a hormonal therapy for her menopause.

4.2 METHODS OF TREATMENT ASSIGNMENT AND BLINDING

Randomization and blinding will be employed to minimize bias in treatment assignment and to provide the basis for valid statistical inference. Eligible patients must be randomized through IxRS prior to receiving any study drug. Patients who discontinue treatment for any reason will not be replaced. Under no circumstances are patients who enroll in this study and who have completed treatment as specified, permitted to be re-randomized to this study.

The randomization list will not be available to the study centers, monitors, project statisticians, or to the Sponsor project team. All individuals directly involved in the study will remain blinded to the treatment assignment until the primary analysis.

To maintain integrity of the trial results and to prevent potential unblinding of the assigned arm during the double-blind treatment phase as a result of adverse events or changes to laboratory results, the following additional measures will be implemented until the time of the primary analysis:

- To prevent potential unblinding as a result of adverse events or laboratory changes, a “**dual assessor**” approach will be used to evaluate efficacy and safety. **Each site will have two blinded investigators: a principal or Treating Investigator and a rating or Examining Investigator.**

The Treating Investigator will be the safety assessor and should be a neurologist with experience in the care of patients with MS. The Treating Investigator will have access to safety data only and will make all treatment decisions based on the patient’s clinical response and laboratory findings.

The Examining Investigator will be the efficacy assessor and should be a neurologist or other qualified health care practitioner trained and certified in administering and scoring the 9-HPT, Functional System Scores (FSS) and EDSS, and SDMT. **The Examining Investigator (or her/his certified designee) will assess the 9-HPT, EDSS scores (including dysphagia/bladder dysfunction assessments), and SDMT.** Until the primary analysis, the Examining Investigator and their qualified designees (if applicable) will not be involved with any aspect of medical management of the patient and will not be allowed access to patient data.

The Treating Investigator and the Examining Investigator will not be allowed to switch roles. Until the primary analysis, an investigator/site staff at a single site may not be a treating investigator for some patients and an examining investigator for others.

- Patient education: During the double-blind treatment phase, prior to being examined by the Examining Investigator, patients should be instructed not to discuss with the Examining Investigator what (if any) adverse effects they may be experiencing.
- Blinded, central MRI assessments: During the double-blind treatment phase, a blinded, central MRI reader will assess all MRI scans performed during the study. Of note, screening and baseline scans will be used for the assessment of patient eligibility, and therefore they will not be blinded.
- Blinding of laboratory parameters: Selected laboratory parameters that may lead to unblinding of the treatment assignment, such as flow cytometry assessment of cell counts including CD19+ cells, lymphocyte count, and Ig levels will be blinded in all patients until the primary analysis. To ensure patient safety during the study and to allow for assessments of the re-treatment criteria, a central laboratory will provide study investigators and the Medical Monitor(s) with reflex messages triggered by abnormal blinded laboratory results and will be instructed to suspend further treatment with study drug until the patient becomes eligible for ocrelizumab re-treatment. Investigators will be notified of their patient's abnormal laboratory test results. Consult the laboratory manual for additional information.
- Ocrelizumab and placebo treatment allocation will remain blinded until the primary database lock for the primary analysis.

To facilitate analysis of the biological samples collected in this study, the treatment code will be released to the responsible analytical person when the samples have been received at the analytical site and are ready for assay. The result of the analysis must not be released with individual identification of the patient until after the unblinding for the primary analysis.

Study site personnel and patients will be blinded to treatment assignment until after the primary analysis. The Sponsor and its agents will also be blinded to treatment assignment, with the exception of individuals who require access to patient treatment assignments to fulfill their job roles during a clinical trial. These roles include the

unblinding group responsible, clinical supply chain managers, sample handling staff, IxRS service provider, and iDMC members.

While PK and ADA samples must be collected from patients assigned to the comparator arm to maintain the blinding of treatment assignment, PK and ADA assay results for these patients are generally not needed for the safe conduct or proper interpretation of this study. Laboratories responsible for performing study drug PK and ADA assays will be unblinded to patients' treatment assignments to identify appropriate samples to be analyzed. PK samples from patients assigned to the comparator arm will not be analyzed for study drug PK concentration except at baseline or by request (e.g., to evaluate a possible error in dosing). ADA samples will be analyzed for all patients treated with study drug.

If unblinding is necessary for a medical emergency (e.g., in the case of a serious adverse event for which patient management might be affected by knowledge of treatment assignment), the investigator will be able to break the treatment code by contacting the IxRS. The investigator is not required to contact the Medical Monitor prior to breaking the treatment code *in an emergency situation. However, the Medical Monitor should be informed that the treatment code has been broken.*

The investigator will also be able to break the treatment code to determine the suitability of subsequent medical care for a patient. However, approval must be obtained from the Medical Monitor if the investigator wants to break the treatment code to determine patient's eligibility for a subsequent clinical trial testing investigational medicinal products or procedures. The investigator must contact the Medical Monitor prior to breaking the treatment code for any reason other than a medical emergency. The investigator should document and provide a justification for any non-emergency unblinding.

As per health authority reporting requirements, the Sponsor's Drug Safety representative will break the treatment code for all serious, unexpected suspected adverse reactions (see Section 5.7) that are considered by the investigator or Sponsor to be related to study drug. The patient may continue to receive treatment, and the investigator, patient, and Sponsor personnel, with the exception of the Drug Safety representative and personnel who must have access to patient treatment assignments to fulfill their roles (as defined above), will remain blinded to treatment assignment.

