6.8 BIOMARKER ANALYSES

Biomarkers will be assessed at baseline and subsequent timepoints following administration of ocrelizumab. Pharmacodynamic biomarkers will be presented as absolute value over time and/or percent change relative to baseline over time and/or proportion of participants with biomarker levels within a defined threshold over time. Biomarker levels at baseline or over time may be compared with efficacy or safety measurements to assess prognostic or predictive properties. Descriptive or summary statistics will be used to describe biomarker assessments.

NfL treatment response will be presented as absolute values over time, percent change relative to baseline over time, and/or proportion of participants with NfL levels below a pre-defined threshold over time.

Baseline NfL levels or NfL levels on treatment determined by the appropriate assay and to be determined pre-defined cutoffs will be used to assess the relationship of baseline or on-treatment NfL to future efficacy, imaging, or other outcomes.

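### The rule releasing the treatment code to assay analysts covers all biological samples, although a specific need is given only for PK and ADA, and it is not reconciled with the blinding statements around it

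*Protocol*

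**What the plan says.** Protocol 4.2 (Methods of Treatment Assignment and Blinding) makes five statements that bear on this point. SAP 1.2.1 repeats them in nearly the same words.

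- General rule: "All individuals directly involved in the study will remain blinded to the treatment assignment until the primary analysis".
- Code release, for the purpose of facilitating the analysis of biological samples: "the treatment code will be released to the responsible analytical person when the samples have been received at the analytical site". It applies once a sample is ready to be assayed, and no sample type is excluded.
- Limit on results: "The result of the analysis must not be released with individual identification of the patient until after the unblinding for the primary analysis".
- Potentially unblinding laboratory parameters: "flow cytometry assessment of cell counts including CD19+ cells, lymphocyte count, and Ig levels will be blinded in all patients until the primary analysis". A central laboratory sends reflex messages when such a result is abnormal.
- PK and ADA: "Laboratories responsible for performing study drug PK and ADA assays will be unblinded to patients' treatment assignments to identify appropriate samples to be analyzed". The reason is that comparator-arm results are generally not needed.

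Protocol 4.2 also lists roles that have access to treatment assignments: the unblinding group, supply chain managers, sample handlers, the IxRS vendor and iDMC members.

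Protocol 4.5.11 describes the samples taken: haematology, chemistry, flow cytometry, immunoglobulins, ADA, plasma and serum for NfL and other biomarkers, and CSF.

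**The concern.** The release sentence is wider than the need behind it. PK and ADA laboratories have to know the arm because they do not run every sample. That reason does not carry over to NfL, cell counts or immunoglobulins, which are reported for both arms.

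An analyst who knows the arm can let it influence repeats, handling of out-of-range values, rejection of poor samples and run order. If that happens, the between-arm contrast is distorted at source and later analysis cannot repair it. The results exposed are NfL (its course by arm and its prognostic or predictive relation to efficacy), other blood and CSF biomarkers and, depending on how the blinding clause is read, B- and T-cell counts and immunoglobulins. Code held without need is also one more place from which it can spread.

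**Working it through.** No arithmetic settles this point. It turns on who may hold the code, so the passages are set side by side.

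**Step 1: scope of the release.** The sentence speaks of the samples collected in the study, without restriction. Protocol 4.5.11 shows that this goes well beyond PK and ADA.

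**Step 2: reasons given.** The release sentence has a purpose, but only a general one (facilitating analysis). A purpose that explains why an analyst must know the arm appears once, for PK and ADA.

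**Step 3: does that reason extend to other assays?** No. Protocol 6.8 states that "NfL treatment response will be presented as absolute values over time", and SAP 4.6.6 presents biomarkers for the safety analysis set, which contains both arms. SAP 4.5.10 summarises laboratory data, including immunoglobulins and T-cell subtypes, and relates immunoglobulin falls to serious infections within each arm. These assays are needed from both arms, so there is no selection to make.

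**Step 4: is the analyst blinded anywhere else?**

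| Measurement | What the documents say about the person measuring | Position |
|---|---|---|
| 9-HPT, EDSS | Blinded Examining Investigator (Protocol 4.2) | Blinded |
| MRI | Central reading centre blinded (Protocol 4.5.10, SAP 1.2.2) | Blinded |
| PK, ADA | Laboratory unblinded, reason given (Protocol 4.2) | Unblinded, justified |
| Flow cytometry, lymphocytes, immunoglobulins | Parameters blinded; analyst not mentioned (Protocol 4.2) | Ambiguous |
| NfL, CSF, other biomarkers | Only the general code release applies | Code release permitted |

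**Step 5: internal consistency.** The general rule and the release sentence cannot both hold literally, because an analyst working on study samples is directly involved. The role list does not resolve this. It names neither the biomarker analysts nor the PK and ADA laboratories, which are unblinded by an explicit sentence nearby. Protocol 4.5.11 also allows biomarker and leftover CSF samples to go to the Sponsor for analysis. The literal release could then reach Sponsor staff, whom Protocol 4.2 keeps blinded unless their role requires access.

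**Step 6: how many samples.** Appendix 1 plans biomarker draws at Weeks 0, 2, 12, 24, 48, 72, 96 and 120, which is 8 per patient, or 9 if a Week 144 draw is counted. With about 1000 patients that is 8 × 1000 = 8,000 to 9 × 1000 = 9,000 sampling occasions before dropout. This shows the reach of the rule. It says nothing about bias.

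**The case against.** The strongest reply is that the passages can be read together. The later paragraph names the laboratories that are unblinded and says why, and the general rule keeps everyone else blinded. The broad sentence may therefore describe only the PK and ADA release. This is a fair reading, and it means that unblinded NfL assay is permitted by the text, not established as practice. It does not rescue the wording, because nothing in the release sentence ties it to PK and ADA.

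Several other points stand.

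- A reader might infer that the release has no stated reason at all. It has one; what is missing is a reason specific to assays other than PK and ADA.
- A reader might infer that flow cytometry and immunoglobulins are assayed unblinded. The documents do not say so, since they call these parameters blinded. Flow cytometry is run on fresh whole blood (Appendix 1), so holding samples back to run the arms separately is implausible. B cells are depleted by 14 days (Protocol 5.1.1.1), so the CD19 result largely reveals the arm anyway.
- A reader might infer a leak to sites through the reflex messages. These are triggered by abnormal results, not by the code, and patient-identified results may not be released before the primary unblinding.
- Rules on repeats, rejection and run layout may well sit in the laboratory manual or the Biomarker Analysis Plan, which are not available here. Their absence from the protocol is not evidence that they do not exist.

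**Conclusion.** The point holds as a drafting defect with modest consequences. Both documents state a rule that allows avoidable unblinding of NfL, CSF and other biomarker analysts, conflicts with the general blinding statement, and leaves flow cytometry, lymphocyte counts and immunoglobulins unclear.

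Its reach is limited. NfL is an exploratory endpoint, and SAP 4.6.6 describes biomarkers with descriptive or summary statistics. For immunoglobulins and T-cell subtypes, Protocol 6.5 plans a mixed model by treatment arm, whereas SAP 4.5.10 gives summaries and SAP 1 says that the SAP supersedes. The efficacy hierarchy rests on 9-HPT, EDSS and centrally read MRI, each with a blinded assessor. A reader might infer a threat to the primary or secondary endpoints, or a quantifiable shift in the NfL contrast. The documents support neither. They give no assay variability and no run plan, so any percentage would be an assumption restated as a result.

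The conclusion rests on the literal wording. If the laboratories already work blinded, the defect lies in the text alone.

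**What to change.** In Protocol 4.2 and SAP 1.2.1, replace the general release sentence with wording such as:

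> Before the primary analysis, the treatment code will be released only to the laboratories performing the ocrelizumab PK and ADA assays. All other assays, including NfL, CSF markers, flow cytometry, haematology and immunoglobulins, will be run by staff blinded to treatment assignment until the primary analysis. Any exception will be listed here with its reason.

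Then reconcile the surrounding text:

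- qualify the statement that everyone directly involved stays blinded, so that it excepts the named roles;
- add the PK and ADA laboratories to the list of those roles;
- say in the clause on flow cytometry, lymphocyte counts and immunoglobulins that the analyst does not hold the code.

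The existing bar on patient-identified results should stay. If any other assay has already been run with the code in hand, record which one in the SAP or the study report.

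The cost is a few sentences in each document, with a matching line in the laboratory manual if needed. No samples, visits or staff are added. The protocol wording needs an amendment, so it is best carried in the next one.

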4.3 STUDY TREATMENT AND OTHER TREATMENTS RELEVANT TO THE STUDY DESIGN

The investigational medicinal product (IMP) for this study is ocrelizumab and matching placebo used to maintain the blind.

4.3.1 Study Treatment Formulation, Packaging, and Handling

4.3.1.1 Ocrelizumab and Placebo

Ocrelizumab will be supplied by the Sponsor in 15 cc Type I glass vials as a sterile, single-use solution for IV infusion and contains no preservatives. Each vial contains 300 mg of ocrelizumab, at a nominal fill volume of 10 mL. The drug product is formulated as 30 mg/mL ocrelizumab in 20 mM sodium acetate at pH 5.3, with 106 mM trehalose dihydrate and 0.02% polysorbate 20. Ocrelizumab may contain fine translucent and/or reflective particles associated with enhanced opalescence. Do not use the solution if discolored or if the solution contains discrete foreign particulate matter. The infusion solution must be administered using an infusion set with an in-line, sterile, non-pyrogenic, low-protein-binding filter (pore size of 0.2 micrometer or less). For information on the formulation and handling of ocrelizumab, see the Ocrelizumab Investigator's Brochure, local prescribing information, and Drug Preparation Guidelines.

In this study, ocrelizumab-matching placebo will be supplied by the Sponsor. The placebo will have the same composition and configuration as the drug product but will not contain ocrelizumab. Ocrelizumab placebo solutions for IV administration will be prepared by dilution of the ocrelizumab placebo into infusion bags containing 0.9% sodium chloride, using an identical procedure as for the active product.

4.3.1.2 Non-Investigational/*Auxiliary* Medicinal Products

In this study, non-investigational/*Auxiliary* medicinal products will include premedication to the ocrelizumab infusion. The following premedication will be used:

- Mandatory methylprednisolone (or an equivalent)
- Mandatory antihistaminic drug (e.g., diphenhydramine)
- Recommended oral analgesic/antipyretic (e.g., acetaminophen 1 g)

Refer to Section [4.3.2.2](#) for further details on premedication administration.

4.3.2 Study Treatment Dosage, Administration, and Compliance

The treatment regimens are summarized in Section [3.1](#). Any dose modification should be noted on the Study Drug Administration Electronic Case Report Form (eCRF). Cases of accidental overdose or medication error, along with any associated adverse events, should be reported as described in Section [5.4.4](#).

Guidelines for treatment modification, interruption, or discontinuation for patients who experience adverse events are provided in Section [5.1.4.3](#).

4.3.2.1 Ocrelizumab and Placebo

The ocrelizumab dose administered will be 600 mg every 24 weeks. The first dose of ocrelizumab will be administered as two 300 mg IV infusions given 14 days apart. For the subsequent doses, ocrelizumab will be administered as a single 600-mg IV infusion every 24 weeks. A minimum interval of 20 weeks must be kept between the

ocrelizumab second infusion during the double-blind treatment phase (Dose 1) and the next infusion at double-blind treatment phase (Dose 2). A minimum interval of 22 weeks must be maintained between each dose of ocrelizumab. This dosing regimen is consistent with the dosing regimen used in the ocrelizumab Phase III/IV studies, as well as with the SmPC and the USPI (see [Table 4](#)).

Patients who experience a DPE during the double-blind treatment phase will be given the option to switch to PDP OCR after they completed at least 120 weeks of double-blind treatment (see Section [3.1.1.3](#) for details). To maintain the original blind, PDP OCR will be offered to all patients who qualify, regardless of their original treatment assignment. The first dose of the PDP OCR will be administered as two 300 mg IV infusions (given 14 days apart) 24 weeks after the last dose of blinded study drug. A minimum interval of 20 weeks must be kept between the ocrelizumab second infusion during the PDP OCR (Dose 1) and the next infusion at PDP OCR (Dose 2). A minimum interval of 22 weeks must be maintained between each dose of ocrelizumab.

Patients who are eligible (see Section [3.1.1.5](#)) and wish to enter the OLE phase will receive two 300 mg IV infusions given 14 days apart for the first OLE dose (OLE Dose 1). For subsequent doses, patients will continue open-label treatment with a single IV infusion of 600 mg ocrelizumab every 24 weeks (OLE Doses 2-N; see [Appendix 3](#) for more details).

Ocrelizumab infusions should be initiated and supervised by an experienced professional with access to appropriate medical support to manage severe reactions such as serious IRRs. It is anticipated that the patient will need to stay at the hospital or clinical site for a full day at an infusion visit. Each ocrelizumab 300 mg dose should be administered as a slow IV infusion over approximately 2.5 hours. Each ocrelizumab 600 mg dose should be administered as a slow IV infusion over approximately 3.5 hours.

Table 4 Overview of Ocrelizumab or Placebo Dosing and Schedule

Amount of Ocrelizumab (or Placebo) to Be Administered		Infusion Instructions	
Initial dose (600 mg), divided into two infusions ^a	Infusion 1	300 mg IV in 250 mL 0.9% sodium chloride	
 Initiate the infusion at a rate of 30 mL/hr for 30 minutes. The rate can be increased in 30 mL/hr increments every 30 minutes to a maximum of 180 mL/hr. Each infusion should be given over approximately 2.5 hours.
	Infusion 2 (2 weeks later) ^b	300 mg IV in 250 mL 0.9% sodium chloride	
Subsequent doses (600 mg), ^b once every 24 weeks	Single infusion ^b	600 mg IV in 500 mL 0.9% sodium chloride	
 Initiate the infusion at a rate of 40 mL/hr for 30 minutes. The rate can be increased in 40 mL/hr increments every 30 minutes to a maximum of 200 mL/hr. Each infusion should be given over approximately 3.5 hours.

^a For patients who receive ocrelizumab at study start of the double-blind phase, start PDP OCR, or start OLE.

^b Prior to the next infusion, a clinical evaluation will be performed to ensure that the patient remains eligible for re-treatment.

Note: Before each infusion of ocrelizumab, 100 mg of methylprednisolone IV and an antihistaminic drug will be administered to reduce the potential for infusion-related reactions.

Alternative Shorter Infusion of Subsequent 600 mg Ocrelizumab Doses

If patient did not experience a serious IRR with any previous ocrelizumab infusion, a shorter (2 hour) infusion of 600 mg can be administered for subsequent doses during any treatment phase. This does not apply for any initial dose (i.e., for patients who receive ocrelizumab at study start of the double-blind phase, start PDP OCR, or start OLE). The shorter infusion should be started at a rate of 100 mL/h. This should be escalated at the rates shown in [Table 5](#).

Table 5 Alternative Shorter Infusions of Ocrelizumab 600 mg

Time (minutes)	Infusion Rate (mL/hr)	Maximum Dose per Interval ^a (mg)	Cumulative Dose (mg)
0–15	100	30	30
15–30	200	60	90
30–60	250	150	240
60–120 ^b	300	360	600

^a Assumes that the infusion bag contains 600 mg ocrelizumab in 500 mL 0.9% sodium chloride. Refer to Dose Preparation Guidelines for more information.

^b The shorter infusion of 600 mg ocrelizumab should be completed in approximately 120 minutes (2 hours).

Refer to Section 5.1.1.1 of this protocol and to current version of the IB for further details on the alternative shorter infusion option, including safety information.

Ocrelizumab must not be administered as an IV push or bolus. Well-adjusted infusion pumps should be used to control the infusion rate, and ocrelizumab should be infused through a dedicated line. It is important not to use evacuated glass containers, which require vented administration sets, to prepare the infusion because this causes foaming as air bubbles pass through the solution.

The patient will need to remain at the clinic at every visit for at least 1 hour after the completion of the infusion for observation. After completion of the infusion, the IV cannula should remain in situ for at least 1 hour to allow for administration of drugs intravenously, if necessary, in the event of a delayed reaction. If no adverse events occur during this period of time, the IV cannula may be removed, and the patient may be discharged.

